13.3 Stratification Factors

No additional stratification will be utilized in this trial.

13.4 Analysis of Secondary Endpoints

Secondary endpoints including disease free and overall survival will be analyzed by Kaplan-Meier method. All of the analyses will be considered exploratory in nature.

13.5 Reporting and Exclusions

13.5.1 Evaluation of toxicity. All patients will be evaluable for toxicity from the time of their first treatment with metformin.

13.5.2 Evaluation of response. All patients included in the study must be assessed for response to treatment, even if there are major protocol treatment deviations. Each patient will be assigned one of the following categories:

1) complete response, 2) partial response, 3) stable disease, 4) progressive disease, 5) early death from malignant disease, 6) early death from toxicity, 7) early death because of other cause, or 9) unknown (not assessable, insufficient data). [Note: By arbitrary convention, category 9 usually designates the “unknown” status of any type of data in a clinical database.] All of the patients who met the eligibility criteria (with the possible exception of those who received no study medication) should be included in the main analysis of the response rate. Patients in response categories 4-9 should be considered to have a treatment failure (disease progression). Thus, an incorrect treatment schedule or drug administration does not result in exclusion from the analysis of the response rate. Precise definitions for categories 4-9 will be protocol specific.

All conclusions should be based on all eligible patients. Subanalyses may then be performed on the basis of a subset of patients, excluding those for whom major protocol deviations have been identified (e.g., early death due to other reasons, early discontinuation of treatment, major protocol violations, etc.). However, these subanalyses may not serve as the basis for drawing conclusions concerning treatment efficacy, and the reasons for excluding patients from the analysis should be clearly reported. The 95%

confidence intervals should also be provided.

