13.0 STATISTICAL CONSIDERATIONS

13.1 Study Design/Endpoints

This is a single arm combination Phase I/II trial of Metformin to determine the maximum tolerated dose (MTD) of metformin among 2 dose levels (850mg, 1500mg administered orally, twice daily) and to evaluate the disease response rate at the MTD. Standard of care conventional chemotherapy (cisplatin) will be administered using current clinical protocols. Dose-limiting toxicity will be ascertained using the Common Terminology Criteria for Adverse Events v4.0. The dose-limiting toxicities ascertained for the phase I component will be gastrointestinal toxicity and hypoglycemia requiring dose reduction. The primary outcome for the phase II component will be disease response rate (RECIST criteria) at 8-12 weeks post treatment completion.

The secondary outcomes will be disease free and overall survival. All analysis of secondary studies will be performed post hoc and will not be used to influence clinical decision making during the therapeutic trial.

This study began as a Phase I “3+3”/ Phase II “Simon” design, but was converted into Bayesian Optimal Interval (BOIN) design before completion of the Phase I to provide monitoring of toxicity beyond the Phase I cohort. BOIN design has algorithmic escalation/de-escalation rules easy to implement like a traditional 3+3 design but allows for specification of the target DLT rate, different size cohorts, is more likely to correctly select the MTD and allocate more patients to the MTD and expands consistent toxicity monitoring to the entire cohort. BOIN design with a target DLT rate of 0.3 and cohort size of 3 begins exactly in the same fashion as the “3+3” allowing for the implemented design change in early stages. Calculations were done using R package BOIN.³²

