A response rate $\geq 60\%$ would be considered effective for patients undergoing metformin plus standard of care, while a response rate $\leq 40\%$ is not considered as effective. The phase II portion of the trial would require at least 28 evaluable patients treated at the MTD. For the purposes of this study, a response will be defined as overall complete response (CR) or overall partial response (PR) (see Table in section 12.1.4.3). Stable disease or progressive disease will be defined as a non-response. The criterion for significance (alpha) has been set at 0.10. The test is 1-tailed, which means that an effect in one direction (improvement) is expected and will be interpreted. Calculation are based on the assumptions of uniform accrual over time. With the proposed sample size of 28 patients the study will have power of 80% to yield a statistically significant result. The treatment strategy (metformin plus standard of care) is considered effective if 17 or more responses are observed among the 28 patients.

Total study sample size.

This study will enroll at least 3 patients at each dose level and at least 28 patients at the MTD level. Participants will continue to be enrolled and monitored for toxicity according to the rules specified above until 28 efficacy evaluable participants have been enrolled to any single dose level. For the purposes of this analysis, a subject is considered evaluable for the primary endpoint after completing at least one dose of Metformin. It is expected that all dose levels will be safe and assuming that even the highest dose level has a DLT rate substantially lower than the target (i.e. $<10\%$), which is what we expect, we will have more than 99% chance of selecting the top dose level at the end of the trial. In this case the total number of patients enrolled would be 31 (3+28). Retrospective clinical studies have not demonstrated an increase in treatment toxicity for patients undergoing cisplatin for HNSCC while taking metformin. It is anticipated that 1-2 patients per month

will be accrued to the study. Depending on the toxicity, this will allow for completion of study within 33-39 months of study initiation.

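### The main response analysis has no settled denominator (all eligible patients, or 28 at one dose level), and the success count of 17 lacks the stated alpha and power even at 28

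*Combined protocol and SAP*

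**What the plan says.** Section 13.1 gives the phase II aim as "to evaluate the disease response rate at the MTD". Section 13.2 tests a null response rate of 40% against a target of 60%. On the error rate it says "The criterion for significance (alpha) has been set at 0.10", and the test is one-tailed. It claims 80% power with 28 patients. The decision rule is that the treatment strategy "is considered effective if 17 or more responses are observed among the 28 patients".

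The same section enrols "at least 28 patients at the MTD level", continues until one dose level holds 28 efficacy-evaluable patients, and counts a patient as evaluable after one dose of metformin. If the top dose level is selected, it expects a total of 31 (3+28).

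Section 13.5.2 takes patients who met the eligibility criteria, with a possible exception for those who received no study drug, and says they "should be included in the main analysis of the response rate". It then states: "All conclusions should be based on all eligible patients". It does not mention dose level. Subanalyses that drop patients for major deviations may not support efficacy conclusions.

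Three other places bear on who is counted:
- Section 1.0 gives 45 patients in total and a phase II cohort of 20.
- Section 6.1 requires at least 70% of the planned metformin dose for response evaluability. It also says the study will forgo dose level 2 and run phase II at dose level 1.
- The footnotes to the dose table in 13.2 say the study had already escalated to the highest dose when the design changed.

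**The concern.** A single-arm trial with a binary endpoint rests on two things: who is in the denominator, and how many responses count as success. Here the first is described in two ways and the second is fixed for one value of the first.

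Read literally, 13.5.2 lets patients from any dose level into the primary rate, while 13.1 and 13.2 ask about one dose level. The same 17 responses are 17/28 = 60.7% of one set and 17/31 = 54.8% of the other. The plan does not say whether 17 still applies to 31, so the choice could be made after the data are seen. A rate pooled over dose levels would also not answer the stated question about the MTD. In addition, Section 4.0 (item a) applies its HPV and smoking restriction only to phase II, so pooling could mix two differently selected groups.

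The count itself also needs checking, because a bare number has the claimed error rates only if it was derived for that denominator.

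**Working it through.** **Inputs (all from 13.2).** Null rate p0 = 0.40, target rate p1 = 0.60, one-sided alpha 0.10, power 80%, N = 28, success at 17 or more.

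**Step 1: reproduce N.** Normal approximation for one proportion, with variance 0.40 × 0.60 = 0.24 under both rates:

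n = (z₀.₉₀ + z₀.₈₀)² × 0.24 / (0.60 − 0.40)² = (1.2816 + 0.8416)² × 0.24 / 0.04 = 27.05, rounded up to 28.

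So 28 is reproduced, and the same approximation gives power of 81.0%. Its critical count is 28 × 0.40 + 1.2816 × √(28 × 0.24) = 11.2 + 3.32 = 14.5, that is 15 responses, not 17.

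**Step 2: the stated rule at 28, exact binomial.** Alpha = P(X ≥ c | 28, 0.40) and power = P(X ≥ c | 28, 0.60).

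| Cut-off c | Alpha | Power |
|---|---|---|
| 15 | 0.1025 | 81.3% |
| 16 | 0.0499 | 69.5% |
| 17 (plan) | 0.0215 | 55.1% |

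The cut-off of 17 gives neither the stated alpha nor the stated power. A futility stage would only lower both figures, so the former two-stage design does not explain it. The target rate times N is 0.60 × 28 = 16.8, so 17 may be the target rate used as the cut-off. That is an inference; the plan gives no derivation.

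**Step 3: keep the count at 17 and let the denominator grow.** Alpha = P(X ≥ 17 | n, 0.40), with every patient assumed to respond with probability 0.40.

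| n | Alpha with a fixed 17 | Smallest cut-off with alpha ≤ 0.10 | Power of that cut-off |
|---|---|---|---|
| 28 | 0.0215 | 16 | 69.5% |
| 31 (3+28, 13.2) | 0.0677 | 17 | 78.1% |
| 32 | 0.0920 | 17 | 83.5% |
| 33 | 0.1211 | 18 | 79.4% |
| 45 (total in 1.0) | 0.6728 | 23 | 91.4% |

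Thirty-three is the first size at which a fixed 17 passes 0.10.

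**Step 4: the other way to carry the rule over.** Scaling the proportion gives 31 × 17/28 = 18.8, so 19 responses. At n = 31 that has alpha 0.013 and power 52%. With 17 or 18 responses among 31, the conclusion therefore depends on whether the count or the proportion is carried over. The plan is silent on this.

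**The case against.** The strongest reply is that 13.5.2 guards against dropping patients for protocol deviations and does not order dose levels to be pooled. Its own explanation concerns incorrect schedules and drug administration, and it contrasts the full set with subanalyses that exclude deviators. Read with 13.1 and 13.2, it can mean all eligible patients within the MTD cohort. On exposure the two sections largely agree: at least one dose in 13.2, untreated patients possibly excluded in 13.5.2. This reading is reasonable, and it means the text does not amount to an instruction to pool. But it has to be supplied by the reader, because 13.5.2 has no dose-level limit.

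A second reply is that there may be no other dose level to pool. Section 6.1 forgoes dose level 2, and the total of 31 assumes that the top level is selected. However, the footnote in 13.2 says the study had already escalated to the highest dose. The documents do not settle the matter.

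A reader might infer that the plan inflates the type I error above 0.10. The documents do not support that. They tie 17 to no denominator other than 28, and alpha is below 0.10 at both 28 and 31. The 45 in Section 1.0 is an enrolment total, set beside a phase II cohort of 20, and is nowhere an analysis denominator. The figures from 33 upward also assume that added patients respond with probability 0.40. Patients whom 13.5.2 counts as failures would add no responses.

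**Conclusion.** Wrong as written, in two respects. First, the denominator of the main response analysis is not reconciled between 13.5.2 and 13.1/13.2, and the success count is undefined for any number other than 28, although 13.2 itself allows more. Second, the count does not match its stated properties at 28: exact alpha is 0.0215 against 0.10, and power is 55.1% against 80%.

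At the documented sizes the error is towards conservatism. At the target rate of 60%, the rule would miss an effective treatment about 45% of the time (1 − 0.551) instead of the intended 20%. Alpha above 0.10 is only a conditional risk, from 33 patients upward against an unchanged 17.

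The second respect rests only on the inputs in 13.2 and the exact binomial distribution. The practical effect of the first depends on how many patients are finally enrolled and at which dose levels, which the documents do not fix.

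**What to change.** - **Section 13.5.2:** define the main response analysis as eligible patients who received at least one metformin dose at the phase II dose level, whatever their later deviations. Report other dose levels separately and descriptively.
- **Section 13.2:** replace the count with an exact one-sided binomial test of 40% at alpha 0.10 on the number in that set, and restate the operating characteristics. At 28 the cut-off is 16 (alpha 0.050, power 69.5%). A cut-off of 15 gives power 81.3%, but its alpha of 0.1025 is slightly over the limit. At 31 the cut-off is 17 (alpha 0.068, power 78.1%). If both stated targets are to be met exactly, 30 patients with a cut-off of 16 would do so (alpha 0.097, power 82.5%).
- **Reconcile** Sections 1.0, 6.1 and 13.2 on the dose level used for phase II, the total number of patients and the 70%-of-dose evaluability criterion, and bring the response set in 13.5.2 into line with the result.

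The cost is a few sentences of protocol text and, unless 30 patients are chosen, no added patients. There are three downsides. Patients at other dose levels leave the primary test. The cut-off at 28 falls from 17, a change to the success rule that should be documented and made without reference to response data. The claimed 80% power at 28 must be replaced by a lower figure.

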14.0 DATA MANAGEMENT

Subjects will be assigned a 4-digit study number (study ID) by the OnCore system which is the Clinical Trials Monitoring system utilized by the DLDCCC. The study number will not contain any identifiers. Study numbers will be assigned sequentially starting at “0001”. The study number list will be stored electronically and only accessible to authorized study personnel. Physical research data (including patient records and consent forms) will be secured in a confidential manner in a locked room at the appropriate clinic/hospital, and in secure manner in the DLDCCC offices ([name]). Electronic research data will be stored at BCM on BCM servers which are password-protected. Electronic research data will be kept on a DLDCC-specific shared drive on BCM servers; access is limited to authorized study personnel. Electronic research data will also be kept in the OnCore database on BCM secure server with limited user-specific, password-protected access. Data are entered into the web application by authorized research personnel via secure HTTPS connections. BCM Research staff are authenticated securely with BCM’s LDAP/Active Directory. BCM IT maintains a firewall, intrusion protection service, and F5 Big IP servers for further protecting data within OnCore. All hardware systems are housed in HIPAA-compliant facilities that have 24-hour guards and access restricted by proximity cards and keys.

12.1 Study Documentation

Flow sheets documenting dates and doses of therapy as well as clinical chemistries, hematological parameters, the clinical status and occurrence of any adverse events and subsequent interventions are to be kept on all patients.

- Imaging reports
- Clinic notes
- Laboratory reports
- Surgical summaries
- Autopsy summaries, where appropriate
- Informed consent documents

12.2 Clinical Data Management and Analysis

All required clinical evaluation records are the responsibility of the study Principal Investigator, [name], who will also be responsible for analysis of the clinical outcome and toxicity.

15.0 QUALITY ASSURANCE

This study will be monitored by the DLDCC Quality Assurance program for study conduct and quality of data, according to CTSU policy. Protocol compliance, eligibility verification, informed consent procedure verification and data accuracy will be monitored.

16.0 DATA AND SAFETY MONITORING

This study will be reviewed regularly by the Data Review Committee of the Dan L. Duncan Comprehensive Cancer Center, in accordance with the DLDCCC Data and Safety Monitoring Plan. The Data Review Committee will monitor the study for progress and enrollment, toxicities, adverse events, and soundness of data.

The frequency of data review by the DRC is determined by the Protocol Review and Monitoring Committee at the time of initial review and is based on the level of risk to the study subjects. Information reviewed by the committee includes:

- a. Overall protocol accrual and expected number of patients to be treated
- b. Patient registrations with regard to eligibility and evaluability
- c. All adverse events and their relationship to the protocol therapy (e.g., by dose level, treatment arm, etc.), in order to determine if participants are being exposed to unanticipated or excessive toxicity
- d. All serious adverse events or unanticipated problems requiring expedited reporting as defined in the protocol
- e. Results of any planned interim analyses
- f. Response evaluations, if relevant
- g. Any issues with protocol conduct or compliance
- h. Status of participation rate in correlative biology and/or imaging studies, if applicable
- i. Study amendments or modifications that may have occurred since last review
- j. Date of next planned review

17.0 PROTECTION OF HUMAN SUBJECTS

This is a voluntary study and all patients will undergo informed consent prior to participation. Patients will be allowed to withdraw from the study at any time; all patient data and samples will be destroyed at patient request upon withdrawal from the study. Patients will not be offered financial or other inducements to participate in the study. All patients who wish to receive standard of care in lieu of study participation will be offered standard of care treatment consistent with national guidelines and institutional standards.

Retrospective studies have demonstrated that patients taking metformin during chemo-radiation demonstrate improved response to conventional treatment and improved survival. No prospective studies to date have confirmed this effect, hence the current proposal. It is possible that patients enrolled in this study will in fact demonstrate improvement in clinical outcomes as detailed in the study. However, we would not expect that every individual patient in this trial will experience a clinical benefit from the proposed study.

This is the first and only (to date) proposed, prospective clinical trial testing the hypothesis that metformin can improve clinical outcomes in patients undergoing chemo-radiation for head and neck cancer. If our hypothesis is proven to be correct, it is possible that metformin will be incorporated into future clinical practice following additional prospective validation

of our results. Introduction of a cheap, readily available drug, with proven clinical effectiveness, would greatly impact large numbers of patients with head and neck cancer.

The risks associated with this clinical trial are relatively small. Although metformin, the investigational drug, can generate some systemic toxicity (i.e. gastrointestinal disturbances), the expected toxicity from current standard of care regimens consisting of chemo-radiation (i.e. xerostomia, mucositis, nausea, vomiting) greatly exceeds that of the investigational agent. Furthermore, clinical outcomes for the patient subset included in this study remain poor. As such, the potential to identify an effective potentiator of chemo-radiation effectiveness, with relatively low expected toxicity should outweigh the risks associated with conducting the trial.

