6.5 Criteria for Removal from Study

Criteria for removal from the study include: intercurrent illness that prevents further treatment administration, patient's decision to withdraw from the study, progression of disease, development of a 2nd primary tumor (lung, esophagus, oral cavity, oropharynx, larynx or hypopharynx) and delay in protocol initiation and/or completion. If the protocol is discontinued, all patient follow up will continue in accordance with institutional standard of care protocols.

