18.2 Adverse Event Reporting

- 18.2.1 All adverse events (all grades), regardless of perceived relationship to study treatment, will be reported and recorded on the appropriate CRFs. New AEs and SAEs that are ongoing at the end of the study will be followed for 30 days from the patient's receipt of the last dose of protocol therapy, unless they have resolved earlier. SAEs and drug related AEs ongoing at the end of study will be followed until resolution.
- 18.2.2 The AE description will include the nature of the experience, the date of onset, the resolution date, the severity of each sign or symptom reported using the NCI-CTCAE (version 4.0), the seriousness of the event, the potential relationship to study treatment, the course of action taken, and the outcome of the experience.
- 18.2.3 Serious adverse events are to be reported to the institutional review board (IRB) according to each board's reporting requirements and required time frame.
- 18.2.4 The Study Chair/Principal Investigator will be responsible for reporting all adverse events to the FDA as per their reporting requirements and time frame.
- 18.2.5 Any event that is reportable to the BCM IRB must also be reported to the DLDCCC Data Review Committee (DRC), via the Patient Safety Officer at [contact].

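### Section 17 allows all data of a withdrawing patient to be destroyed on request, which conflicts with the analysis populations in 13.5.1 and 13.5.2; the effect on the decision rules is conditional and modest for a few patients

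*Combined protocol and SAP*

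**What the plan says.** Section 17.0 states that "all patient data and samples will be destroyed at patient request upon withdrawal from the study". The wording covers data as well as samples and does not separate data already collected from data still to come. Withdrawal is foreseen: section 6.5 lists the "patient's decision to withdraw from the study" among the reasons for removal. Sections 6.5, 13.5, 14, 16, 18 and 19 contain no rule that keeps data collected before withdrawal.

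The analysis sections assume that the records exist:

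- 13.5.1: "All patients will be evaluable for toxicity from the time of their first treatment with metformin".
- 13.5.2: "All conclusions should be based on all eligible patients". Response categories 4 to 9, which include unknown status (category 9), count as treatment failures.
- 13.2: enrolment and toxicity monitoring continue "until 28 efficacy evaluable participants have been enrolled to any single dose level". A patient is evaluable for the primary endpoint after one dose of metformin.
- 18.2.1: "All adverse events (all grades), regardless of perceived relationship to study treatment, will be reported and recorded on the appropriate CRFs".

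**The concern.** For a patient who withdraws and asks for destruction, sections 17 and 13.5 cannot both be followed as written. Once the records are gone, a DLT cannot be shown in the cumulative count behind the 13.2 table, and a documented non-response cannot be shown in the response analysis.

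The loss would depend on the patient's own choice. It is plausible, though not documented, that patients with toxicity or a poor course withdraw more often. In that case the loss would tend to flatter metformin. The trial has a single arm and 28 patients, so no concurrent control group shares the bias, and destroyed records cannot be restored at analysis.

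**Working it through.** **1. The plan's own figures.** Inputs from 13.2: n = 28, success at 17 or more responses, unpromising rate 0.40, promising rate 0.60, one-sided alpha 0.10, stated power 80%. With X binomial:

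- P(X ≥ 17 | 28, 0.40) = 0.0215
- P(X ≥ 17 | 28, 0.60) = 0.551

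The stated 80% does not reproduce with a cutoff of 17. A cutoff of 15 gives power 0.813 with alpha 0.1025. That is a separate matter; the stated cutoff of 17 is used below.

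**2. Non-responders erased and replaced.** The documents give no number of requests, so k = 1 to 3 is an assumed range. If k non-responders among 28 are deleted and k new patients enrolled:

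P(success) = Σₓ P(X = x) · P(Bin(min(k, 28 − x), p) ≥ 17 − x)

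For k = 1 only x = 16 adds to the base. At p = 0.40 this is 0.0215 + 0.0284 × 0.40 = 0.0329. At p = 0.60 it is 0.551 + 0.144 × 0.60 = 0.637.

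| k erased and replaced | true rate 0.40 | true rate 0.60 |
|---|---|---|
| 0 | 0.0215 | 0.551 |
| 1 | 0.0329 | 0.637 |
| 2 | 0.0481 | 0.715 |
| 3 | 0.0677 | 0.781 |

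**3. The loss needed to exceed alpha.** Suppose a share d of non-responders is erased and replaced, and no responder is. The apparent rate at a true 0.40 is 0.4 / (0.4 + 0.6(1 − d)). The chance of 17 or more in 28 is 0.0406, 0.0763 and 0.1413 for d = 10%, 20% and 30%. It crosses 0.10 at d of about 24%. That is 0.6 × 0.243 = 0.146, or about 15% of all enrolled patients, and 28 × 0.146 / (1 − 0.146) = about 5 erased patients for every 28 kept.

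**4. Erasure without replacement.** The number of responses does not change, so the comparison with 17 does not change. Only the rate and its interval move: 16/28 = 57.1% becomes 16/27 = 59.3%, and 16 still falls short.

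**5. Toxicity.** Section 13.1 specifies a "BOIN design with a target DLT rate of 0.3 and cohort size of 3". With the usual BOIN defaults (0.6 and 1.4 times the target), the boundaries are 0.2365 and 0.3585, as 13.2 states. The tabulated counts for 3 to 27 patients also reproduce, with elimination when P(DLT rate > 0.3) > 0.95 under a Beta(1,1) prior. If one DLT is erased and the patient replaced by one without a DLT:

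| Before | After | Change in the table's decision |
|---|---|---|
| 4/6 | 3/6 | eliminate → de-escalate |
| 11/24 | 10/24 | eliminate → de-escalate |
| 9/24 | 8/24 | de-escalate → stay |

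Under the first footnote to the table, a de-escalate signal at the lowest level, without elimination, means three more patients at the same level; elimination there stops the trial. The first two rows therefore matter at any level. The third changes the action only if a lower level is available.

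The documents do not settle whether one is. Section 13.2 evaluates 850 mg and 1500 mg, and a footnote says that the study had escalated to the highest dose. Section 6.1 also lists a level −1, and its note of 12/19/2018 forgoes level 2 and proceeds with level 1. These passages must be reconciled.

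**The case against.** Several stronger readings are tempting, and the documents do not carry them.

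- *The vacated slot will be refilled.* No replacement rule for withdrawn patients is stated. The 13.2 enrolment wording permits replacement, but a patient is evaluable after one dose, so someone who withdraws later may already be one of the 28.
- *The false-positive rate will exceed alpha.* It does so only at d of about 24%, with every erased patient a non-responder and every one replaced. Nothing in the documents supports such a rate.
- *A patient whose data are destroyed cannot be counted as a failure.* Category 9 needs only the fact of enrolment and dosing, and section 17 does not say that this count is erased. A recorded DLT has no such fallback.
- *Section 18.2.1 is breached and safety events are lost.* That section requires recording and reporting, not retention in so many words. Reports already sent to the IRB, the Data Review Committee or the FDA under 18.2.3 to 18.2.5 may survive. This conflict is secondary.
- *The toxicity decision is likely to flip.* Section 13.2 expects a DLT rate below 10%. At 10%, P(9 or more of 24) = 0.0003. A DLT already used in a decision has also had its effect there, although the count at a dose is cumulative and later decisions would lack it.

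The consent pages were not available, so the promise made to patients cannot be checked. What stands is that section 17 has no exception and that 13.5.1 and 13.5.2 depend on data that it lets go.

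**Conclusion.** The conflict between section 17 and sections 13.5.1 and 13.5.2 is real and rests on the text alone. Its consequences are conditional. They require a patient to withdraw and ask for destruction, and for the response decision they also require replacement. Under the assumed range of one to three erased and replaced non-responders, the chance of a false success rises from 2.2% to between 3.3% and 6.8%, within the stated alpha of 0.10. For toxicity, a single patient can change a decision at the elimination boundary, although that boundary is remote at the DLT rate the plan expects. A reader might infer that the trial's conclusions will be biased towards metformin; the documents give neither a withdrawal rate nor a link between withdrawal and outcome, so they do not support that. This is a worthwhile, low-cost improvement that has to be in place before a request is acted on.

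**What to change.** Amend section 17, and any matching consent wording, to say that at withdrawal no new data are collected unless the patient permits it, that unused samples are destroyed on request, and that data collected up to withdrawal are retained and analysed. Add to 13.5 and 13.2 that withdrawn patients who took metformin stay in the 13.5.2 response denominator and that their DLTs stay in the 13.2 count. State also whether withdrawn patients are replaced.

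The cost is a few sentences and an IRB-approved consent revision. Patients who consent under the new wording lose the option to have past data erased; withdrawal itself and destruction of samples are kept. For patients already enrolled, honour the existing promise unless they re-consent. In every case keep the count of treated patients, and class anyone whose data were destroyed as category 9.
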